9.2.2 Study population

Inclusion criteria:

- 1. At least one prescription for Tio+Olo (FDC or free combination) as a new initiation between 1st January 2014 and 31st December 2019.
- 2. Aged \geq 40 years on the index date;
- 3. At least one diagnosis of COPD at any time prior to or on the index date;
- 4. At least one year of continuous medical and health insurance plan prior to the index date will be required to allow for a look-back period for the covariates and identification of new use of the study drugs;
- 5. At least one record in the health insurance system database;

Exclusion criteria:

- 1. Any use of Tio+Olo in free or fixed form within one year prior to the index date;
- 2. Individuals with asthma, allergic rhinitis, lung cancer, interstitial lung disease, or lung transplant identified at any time prior to the index date;

Another cohort of patients using other LAMA/LABAs (FDC or free combination) will also be enrolled to collect the information of baseline characteristics to be compared with those of patients treated with Tio+Olo. The Inclusion/Exclusion criteria are similar with those of Tio+Olo, which include:

Inclusion criteria:

- 1. At least one prescription for LAMA+LABA (FDC or free combination) other than Tio/Olo as a new initiation between 1st January 2014 and 31st December 2019.
- 2. Aged \geq 40 years on the index date;
- 3. At least one diagnosis of COPD at any time prior to or on the index date;
- 4. At least one year of continuous medical and health insurance plan prior to the index date will be required to allow for a look-back period for the covariates and identification of new use of the study drugs;
- 5. At least one record in the health insurance system database.

Exclusion criteria:

- 1. Any use of LAMA+LABA in free or fixed form for one year prior to the index date;
- 2. Individuals with asthma, allergic rhinitis, lung cancer, interstitial lung disease, or lung

NIS Protocol Page 20 of 43 BI Study Number: 1237-0109 c38644780-01

Proprietary confidential information © 2022 Boehringer Ingelheim International GmbH or one or more of its affiliated companies

transplant identified at any time prior to the index date.

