9.5 STUDY SIZE

There will be around 4,000 patients using Tio+Olo in the Taiwan NHIRD that can be enrolled in this study.

Assuming that observed incidence rates of each AE from Ferguson paper could be replicated, and 4000 patients were enrolled in the study in a uniform distribution from 0 to 6 years. The estimation and 95% CI for incidence rate of each AE among new users of Spiolto® Respimat® for the study duration of 6 years were calculated based on Poisson distribution and provided as the following table.

Table 1 Incidence rate of AEs

Adverse events	Incidence	N	95% CI	
	rate per		Lower	Upper
	100			
	patient			
	years			
Pneumonia	4.69	4000	4.308	5.083
COPD	55.42	4000	54.092	56.758
exacerbation				
Arrhythmia	1.82	4000	1.583	2.067
Supraventricul	1.16	4000	0.975	1.358
ar tachycardia				

001-MCS-90-118_RD-23 (2.0) / Saved on: 03 Jul 2020

NIS Protocol Page 25 of 43 BI Study Number: 1237-0109 c38644780-01

Proprietary confidential information © 2022 Boehringer Ingelheim International GmbH or one or more of its affiliated companies

Incidence rate of AEs from Ref: G.T. Ferguson, et al., Respiratory Medicine 143 (2018) 67–73.

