9.9 LIMITATIONS OF THE RESEARCH METHODS

In this study, we will describe the incidence rate of AEs among patients who initiate Spiolto. Patients taking Spiolto might be different from patients taking only

NIS Protocol Page 27 of 43 BI Study Number: 1237-0109 c38644780-01

Proprietary confidential information © 2022 Boehringer Ingelheim International GmbH or one or more of its affiliated companies

maintenance therapies (so-called channelling) in terms of their baseline characteristics, which makes it difficult to interpret the results. To help put the results into perspective, we will compare the baseline characteristics between patients who initiated Spiolto and patients treated with other LAMA/LABAs to understand the potential channelling.

In a database study like this, we can only rely on the available information to define outcomes, exposure and covariates. Misclassification may happen during this process.

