3. PURPOSE AND SCOPE

According to requirement by local regulatory authority, the safety information of newly approved drugs is to be collected to provide supplementary data to those identified in randomized clinical studies within 5 years period after approval. This is a non-interventional study based on existing data. It will provide the safety information of Spiolto (tiotropium+olodaterol) in Chinese patients with chronic obstructive pulmonary disease (COPD) in routine clinical practice in Taiwan.

Statistical and Epidemiological Analysis Plan (SEAP) for Non-Interventional Studies (NIS) Template c40431892-01 Page 5 of 38

Proprietary confidential information © 2022 Boehringer Ingelheim International GmbH or one or more of its affiliated companies

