6.3 STUDY POPULATION

For incident Tio/Olo combined inhaler cohort

• Inclusion criteria:

- 1. At least one prescription for Tio+Olo (fixed dose combination (FDC) or free combination) as a new initiation between 1st January 2014 and 31st December 2019 (the free combination will be defined as the prescriptions of the two compounds on the same day);
- 2. Aged ≥ 40 years on the index date (The first dispensing of Tio+Olo combined inhaler will be defined as the index date);
- 3. At least one diagnosis of COPD (ICD9: 491.x, 492.x, 496; ICD10: J41.x, J42, J43.x, J44.x) at any time prior to or on the index date;
- 4. At least one year of continuous medical and health insurance plan prior to the index date will be required to allow for a look-back period for the covariates and identification of new use of the study drugs;
- 5. At least one record in the health insurance system database.

• Exclusion criteria:

- 1. Any use of Tio+Olo in free or fixed form within one year prior to the index date. (the free combination will be defined as the prescriptions of the two compounds within 30 days);
- 2. Individuals with asthma, allergic rhinitis, lung cancer, interstitial lung disease, or lung transplant identified at any time prior to the index date.

Relevant ICD codes and procedure code are provided in the Annex.

Statistical and Epidemiological Analysis Plan (SEAP) for Non-Interventional Studies (NIS) Template c40431892-01 Page 7 of 38

Proprietary confidential information © 2022 Boehringer Ingelheim International GmbH or one or more of its affiliated companies

For other incident LAMA/LABAs combined inhaler cohort

Inclusion criteria:

- 1. At least one prescription for LAMA+LABA FDC (Vilanterol/Umeclidinium; Indacaterol /Glycopyrronium) or free combination (LABA: Salmeterol; Formoterol; Procaterol; Indacaterol; Olodaterol, LAMA: Tiotropium bromide; Glycopyrrolate; Umeclidinium) other than Tio/Olo as a new initiation between 1st January 2014 and 31st December 2019 (the free combination will be defined as the prescriptions of the two compounds on the same day);
- 2. Aged ≥ 40 years on the index date (The first dispensing of LAMA+LABA combined inhaler will be defined as the index date);
- 3. At least one diagnosis of COPD at any time prior to or on the index date;

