7. VARIABLES

7.1 EXPOSURES

Exposure of this study is defined as new initiation of Tio/Olo or other LAMA/LABA inhaler (FDC or free combination) during the study period. The free form will be defined as the prescriptions of the two compounds on the same day. Drug codes of interest are provided in the Annex.

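### The primary cohort and the visible Table 2 pool the fixed Tio/Olo inhaler with free combinations, so they do not isolate the Spiolto rate that parts of the plan promise

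*SAP*

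**What the plan says.** **Where the plan names the product.** SAP section 3 states the aim: "It will provide the safety information of Spiolto (tiotropium+olodaterol) in Chinese patients". Protocol 9.9 says "we will describe the incidence rate of AEs among patients who initiate Spiolto". Protocol 9.5 describes its precision table as the "incidence rate of each AE among new users of Spiolto® Respimat® for the study duration of 6 years". The protocol abstract header names the finished product as Spiolto Respimat with code R03AL06.

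**Where the plan defines the cohort.** SAP 6.3 requires "At least one prescription for Tio+Olo (fixed dose combination (FDC) or free combination) as a new initiation", and Protocol 9.2.2 has the same rule: "At least one prescription for Tio+Olo (FDC or free combination) as a new initiation between 1st January 2014 and 31st December 2019". SAP 7.1 adds: "The free form will be defined as the prescriptions of the two compounds on the same day". SAP Appendix 2 lists tiotropium as R03BB04 and olodaterol as R03AC19, neither limited by device or strength, and lists the fixed combination separately as R03AL06.

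**Where the plan reports.** The visible Table 2 shell in SAP Annex 1 has one row per event for patients treated with Tio+Olo, with no division into fixed and free.

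**Index date.** SAP 6.3 says: "The first dispensing of Tio+Olo combined inhaler will be defined as the index date".

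**The concern.** The study is a post-authorization safety study whose report goes to health authorities, and its stated reason is to supply safety information on a newly approved product. If the primary table mixes that product with two-inhaler regimens built from any tiotropium preparation, a reader who takes the rates as Spiolto rates is reading a different quantity. The reader also cannot judge how different it is, because the visible shell shows neither the number of free-combination patients nor their person-time.

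The index-date wording adds a smaller problem. Free combinations are eligible, but the index date refers to a combined inhaler. A programmer who took that phrase to mean the fixed product would build a different cohort from one who took it to cover both forms.

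**Working it through.** **1. Reproduce Protocol Table 1, to see which patients it counts.**

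Inputs from Protocol 9.5: 4,000 patients, follow-up uniform on 0 to 6 years, Poisson limits.

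Person-years = 4,000 × (0 + 6)/2 = 12,000. Expected events = rate per 100 × 120. Limits = 2.5% and 97.5% Poisson quantiles, divided by 120.

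| Event | Rate per 100 PY | Expected events | Quantiles | Limits obtained | Limits stated |
|---|---|---|---|---|---|
| Pneumonia | 4.69 | 562.8 | 517, 610 | 4.308, 5.083 | 4.308, 5.083 |
| COPD exacerbation | 55.42 | 6,650.4 | 6,491, 6,811 | 54.092, 56.758 | 54.092, 56.758 |
| Arrhythmia | 1.82 | 218.4 | 190, 248 | 1.583, 2.067 | 1.583, 2.067 |
| Supraventricular tachycardia | 1.16 | 139.2 | 117, 163 | 0.975, 1.358 | 0.975, 1.358 |

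All eight limits match. Protocol 9.5 calls the 4,000 patients Tio+Olo users and then applies all of them to a table described as Spiolto Respimat users. It makes no allowance for free combinations.

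**2. Relate the pooled rate to the Spiolto rate.**

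Let f be the free-combination share of person-time and RR the free rate divided by the fixed rate. Then

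pooled rate = fixed rate × [(1 − f) + f × RR] = fixed rate × [1 + f(RR − 1)].

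The documents give neither f nor RR. The values below are assumptions, chosen to include no effect and effects in both directions. Entries are the percentage by which the pooled rate differs from the Spiolto rate.

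| f | RR 0.8 | RR 1.0 | RR 1.25 | RR 1.5 | RR 2.0 |
|---|---|---|---|---|---|
| 1% | −0.2 | 0 | +0.2 | +0.5 | +1.0 |
| 5% | −1.0 | 0 | +1.2 | +2.5 | +5.0 |
| 10% | −2.0 | 0 | +2.5 | +5.0 | +10.0 |
| 20% | −4.0 | 0 | +5.0 | +10.0 | +20.0 |
| 30% | −6.0 | 0 | +7.5 | +15.0 | +30.0 |

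Example: with a fixed-inhaler pneumonia rate of 4.69 and f = 20%, RR 0.8 gives 4.69 × 0.96 = 4.50 and RR 1.5 gives 4.69 × 1.10 = 5.16.

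**3. Compare with the planned precision.**

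Relative half-widths from Table 1:
- COPD exacerbation: (56.758 − 54.092)/2/55.42 = 2.4%
- Pneumonia: (5.083 − 4.308)/2/4.69 = 8.3%
- Arrhythmia: (2.067 − 1.583)/2/1.82 = 13.3%
- Supraventricular tachycardia: (1.358 − 0.975)/2/1.16 = 16.5%

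A 10% shift exceeds the first two and not the last two. A 5% shift exceeds only the first. Table 1 assumes three years of follow-up on average, whereas the SAP ends follow-up at a 45-day lapse, so the realised intervals are likely to be wider than these.

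**4. Price of a fixed-only row.**

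The method of step 1 is applied to 12,000 × (1 − f) person-years, holding the rates at their Table 1 values.

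| f | Fixed-only PY | Pneumonia limits | Supraventricular tachycardia limits |
|---|---|---|---|
| 0% | 12,000 | 4.308–5.083 | 0.975–1.358 |
| 10% | 10,800 | 4.287–5.102 | 0.963–1.370 |
| 20% | 9,600 | 4.260–5.125 | 0.948–1.385 |
| 30% | 8,400 | 4.238–5.155 | 0.940–1.393 |
| 50% | 6,000 | 4.150–5.250 | 0.900–1.433 |

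Even at a 50% free share the loss of precision is modest.

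**The case against.** **The pooling is consistent and looks deliberate.** The study title, primary objective, primary outcome and Table 2 caption all use the substance names, and both documents define that exposure as fixed or free. Table 2 therefore answers the objective as worded. SAP section 3 itself glosses Spiolto as tiotropium plus olodaterol. This stands. It means the mismatch could be cured by relabelling alone, but not that it is absent: the limitations section and the precision statement still promise rates for starters of the named product.

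**A split may already be planned.** Protocol 9.7.2 and SAP 10.2 are not visible, nor are several pages after SAP Table 3. The protocol's ENCePP checklist points to 9.7.2 for stratified and sensitivity analyses. This stands, and limits the point to the cohort definition and the visible Table 2. A reader should not infer that no fixed-inhaler analysis exists.

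**Stronger readings that the documents do not support.**
- A reader might infer that free-combination users have no index date, and that those who later move to the fixed inhaler are removed by the first exclusion criterion. In context, the SAP uses combined inhaler as an umbrella term. The cohort carrying that name in SAP 6.3 lists free combinations in its first inclusion criterion, and SAP 7.1 attaches both forms to the word inhaler. On that reading, a patient with a same-day pair enters at that date, and the exclusion looks only at the year before it. The wording needs tightening; it does not show lost patients.
- A reader might infer that the Spiolto rates are biased by a known amount. With f and RR unknown, a range that starts above RR = 1 would assume its own conclusion.
- A reader might extend the criticism to the baseline comparison in Table 3. The SAP's secondary objective names fixed or free combinations for the comparator, both cohorts are pooled alike, and the comparison is descriptive. A fixed-versus-fixed version would be a preference.

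**Conclusion.** The point holds as a mismatch between the product that the plan names and the quantity that its visible primary table estimates. Bias is not demonstrated. The size depends on two figures that the documents do not give: nil at RR = 1, about 1% or less at f = 1% for RR between 0.8 and 2, and, for illustration, −4% to +10% at f = 20% for RR between 0.8 and 1.5. Whether it matters against the planned precision depends on the event, with exacerbation the most exposed because its interval is the tightest.

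The conclusion assumes that the sections not visible do not already give rates by formulation. It is worth correcting because the code needed is already listed and the cost is low, but it does not invalidate the primary analysis of Tio+Olo in either form.

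**What to change.** 1. In Table 2, report N, person-years, events and rates for fixed-combination initiators (R03AL06) and for free-combination initiators separately, beside the pooled figure, unless Protocol 9.7.2 or SAP 10.2 already provides this. The follow-up rules do not mention a move from free to fixed, so state to which row the later person-time belongs.
2. Tie each Spiolto statement (SAP section 3, Protocol 9.9, Protocol 9.5 with Table 1) to the R03AL06 row. Alternatively, relabel those statements and Table 1 as Tio+Olo, fixed or free.
3. Reword the index date in SAP 6.3 as the first R03AL06 dispensing or the first same-day pair, so that combined inhaler cannot be read as excluding free combinations.

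Cost: SAP wording and extra rows or columns from data already to be extracted. The fixed-only interval is slightly wider; at a 20% free share, pneumonia goes from 4.308–5.083 to 4.260–5.125 per 100 patient-years. The relabelling route costs no precision, but it leaves the Spiolto question unanswered.

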6.2 SETTING

Data used in this study will come from the Taiwan National Health Insurance (NHI) claims data. Cohort for incident Tio/Olo combined inhaler use would be identified from 2014 through 2019, with a 1-year look-back period to define new user. Cohort for other incident LAMA/LABAs combined inhaler use would be identified from 2014 through 2019, and also with a 1-year look-back period to define new user.

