- 4. At least one year of continuous medical and health insurance plan prior to the index date will be required to allow for a look-back period for the covariates and identification of new use of the study drugs;
- 5. At least one record in the health insurance system database.

[figure not shown]
• Exclusion criteria:

- 1. Any use of LAMA+LABA in free or fixed form for one year prior to the index date (the free combination will be defined as the prescriptions of the two compounds within 30 days);
- 2. Individuals with asthma, allergic rhinitis, lung cancer, interstitial lung disease, or lung transplant identified at any time prior to the index date.

Relevant ICD codes and procedure code are provided in the Annex.

Statistical and Epidemiological Analysis Plan (SEAP) for Non-Interventional Studies (NIS) Template c40431892-01 Page 8 of 38

Figure 1. Patient selection flow chart

Statistical and Epidemiological Analysis Plan (SEAP) for Non-Interventional Studies (NIS) Template

c40431892-01 Page 9 of 38

Proprietary confidential information © 2022 Boehringer Ingelheim International GmbH or one or more of its affiliated companies

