10. DATA ANALYSIS

10.1 MAIN ANALYSIS

All variables, including patient characteristics, baseline measures, and outcomes, will be analyzed descriptively.

- For all analyses, variables will be reported as follows: Continuous variables (e.g., age) will be presented as means (with standard deviation, SD) and/or medians (with interquartile range, IQR), minimum, maximum.
- Categorical variables (e.g., sex) will be presented as absolute and relative frequencies.

We will first describe formation of the study cohort. Patient characteristics at baseline will be described using standard descriptive statistics. Absolute standardized differences (ASDs) will be used to compare the characteristics between the two groups, in which a >0.1 ASD indicates a meaningful difference.

As an objective of the study was to compare the clinical attributes of patients in each study group. The standardized difference will be used as a parameter to quantify the between-group differences for each clinical attribute. This is metric is commonly used in studies utilizing

Statistical and Epidemiological Analysis Plan (SEAP) for Non-Interventional Studies (NIS) Template

c40431892-01 Page 15 of 38

Proprietary confidential information © 2022 Boehringer Ingelheim International GmbH or one or more of its affiliated companies

secondary health data, in which a standardized difference of larger than 0.1 indicates a meaningful difference with respect to the clinical attribute between the two study groups.

For the analysis of primary outcome, the incidence rates of AEs during entire follow-up period will be calculated based on the following formula:

(Total number of patients in the Tio+Olo cohort experiencing an event of interest for the first time during the given time period) / (Total person-time at risk from current use of Tio+Olo during the given period)

[figure not shown]
Number of at-risk patients will be defined for specific adverse outcome of interest, taking into account whether it is a chronic condition for which patients with a prevalent condition are not considered at risk.

For the analysis of the primary outcome, individuals will be followed up from the index date until the earliest of the following

- 1) Outcome of interest
- 2) disenrollment;
- 3) the end of the study period;
- 4) death;
- 5) discontinuation of the index drug use as a lapse of 45 days without subsequent prescription;
- 6) adding ICS mono on top of Tio/Olo.

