ANNEX 1. ADDITIONAL INFORMATION

Table 1. Demographic and cohort entry of the Tio/Olo cohort and LAMA/LABA cohort

	Tio/Olo cohort N=xxxx		LAMA/LABA coho N=xxxx	
	N	%	N	%
Gender				
Male				
Female				
Age				
Mean, SD				
40~59				
60~79				
80+				
Calendar year of cohort entry				
2014				
2015				
2016				
2017				
2018				
2019				
Season of cohort entry date				
Spring (Mar-May)				
Summer (Jun-Aug)				
Fall (Sep-Nov)				
Winter (Dec-Feb)				

Statistical and Epidemiological Analysis Plan (SEAP) for Non-Interventional Studies (NIS) Template

c40431892-01 Page 20 of 38

Table 2. Incidence rate of adverse events in patients with COPD treated with Tio+Olo

Adverse event	No. of events	Person-Years	Incidence rate (per 100 000 person year)	95% CI
Potentially recurrent events				
Nasopharyngitis				
Pneumonia				
Moderate COPD exacerbation				
Severe COPD exacerbation				
Constipation				
Diarrhoea				
Urinary retention				
Urinary tract infection				
Urticaria				
Rash				
Incident events (no occurrence o	f corresponding	g codes during t	the 1-year baselin	ie period)
Arrhythmia				
Myocardial ischemia				
Supraventricular tachycardia				
Glaucoma				
Nonfatal myocardial infarction				
Nonfatal hemorrhagic stroke				
Nonfatal ischemic stroke				
Nonfatal Acute, but ill-				
defined, cerebrovascular				
disease				
Death				

Statistical and Epidemiological Analysis Plan (SEAP) for Non-Interventional Studies (NIS) Template

c40431892-01 Page 21 of 38

Table 3. Secondary outcome (baseline comparison between two study groups)

- ,		1			J & 1)
	Tio/Ol/	o cohort	LAM	A/LABA	
		XXXX	со	hort	Standardized
			N=	XXXX	difference
	N	%	N	%	
COPD treatments in 1 year prior to inde	ex date				
LAMA					
LABA					
ICS					
ICS+LABA free combination					
ICS+LAMA free combination					
LAMA+LABA free combination					
ICS+LAMA+LABA free combination					
ICS/LABA FDC					
LAMA/LABA FDC					
ICS/LAMA/LABA FDC					
Use of other respiratory drugs in 1 year	prior to	index			
date					
Mucolytics					
Theophylline					
Short-acting beta-agonists (SABA)					
Short-acting muscarinic antagonists					
(SAMA)					
Acute COPD exacerbation in 1 year prior	or to inde	x date			
Moderate exacerbation					
0					
1					
>=2					
Severe exacerbation					
0					
1					
>=2					
All exacerbations (Moderate +					
Severe)					
0					
1 >=2					
	c prior to	indov			
Acute COPD exacerbation in the 30 day date	s prior to	inuex			
Moderate exacerbation					
0 1					
>=2					

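### Table 3 compares prior LAMA/LABA FDC use between cohorts whose washouts cover different drugs, so the 0.1 ASD rule should not be applied to that row

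*SAP*

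**What the plan says.** SAP 6.3, exclusion 1 for the Tio/Olo cohort: "Any use of Tio+Olo in free or fixed form within one year prior to the index date". SAP 6.3, exclusion 1 for the comparator: "Any use of LAMA+LABA in free or fixed form for one year prior to the index date". In both, prior free-combination use means the two compounds prescribed within 30 days. Protocol 9.2.2 carries the same pair of exclusions and introduces the comparator's list with "The Inclusion/Exclusion criteria are similar with those of Tio+Olo, which include". SAP 6.2 describes the comparator as identified "also with a 1-year look-back period to define new user".

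Two places bear on what LAMA+LABA means in the comparator's exclusion. SAP Appendix 2 lists the tiotropium/olodaterol FDC in the LABA/LAMA group beside the two comparator FDCs. The comparator's inclusion 2 in SAP 6.3, however, says "The first dispensing of LAMA+LABA combined inhaler will be defined as the index date", where the term can only sensibly mean the comparator products.

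SAP 7.2.2 makes prior LAMA+LABA use, free and fixed, a baseline characteristic; Protocol 9.3.3 had named only the free combinations. In SAP Annex 1, the first block of Table 3 is headed "COPD treatments in 1 year prior to" the index date. It has rows for LAMA/LABA FDC, LAMA+LABA free combination and ICS+LAMA+LABA free combination, by cohort, with a standardized difference. SAP 10.1 reads these differences by a fixed rule, "in which a >0.1 ASD indicates a meaningful difference". Protocol 9.9 gives the purpose: "we will compare the baseline characteristics between patients who initiated Spiolto and patients treated with other LAMA/LABAs to understand the potential channelling".

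**The concern.** The year in which prior dual bronchodilator use decides eligibility is the same year in which Table 3 counts it, and the eligibility rule differs between the cohorts. A patient who used another LAMA/LABA FDC in the past year can enter the Tio/Olo cohort but, at that same index date, cannot enter the comparator. The LAMA/LABA FDC row is therefore shaped by the criteria before any data are seen, yet the 0.1 rule would be applied to it as to any other row.

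At stake is the reading of channelling. Prior treatment is an obvious place to look for it. A gap produced by the exclusion rules could be reported as a meaningful difference between patients; equally, two matching percentages could be reported as balance although they count different drugs.

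**Working it through.** **Inputs.** The plan gives no figure for this row, so there is none to reproduce. The documents supply the expected Tio/Olo cohort of about 4,000 (Protocol 9.5) and the 0.1 threshold (SAP 10.1). The SAP states no ASD formula; I assume the usual one for a binary variable, with p the share in the Tio/Olo cohort and q the share in the comparator:

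ASD = |p − q| / √{[p(1 − p) + q(1 − q)] / 2}

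Neither p nor q is in the documents, so the values below are assumed.

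**Step 1. What each cell of the FDC row can contain, at a given index date.**

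| FDC used in the prior year | Tio/Olo cohort | Comparator, literal reading | Comparator, narrow reading |
|---|---|---|---|
| Tio/Olo | barred | barred | allowed |
| Another LAMA/LABA | allowed | barred | barred |

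On the literal reading, LAMA+LABA includes Tio/Olo, as in SAP Appendix 2. On the narrow reading it means the comparator products only, as the index-date wording suggests. The qualifier on index date matters: the visible text does not stop a patient from entering the comparator at an earlier date and the Tio/Olo cohort later.

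**Step 2. Literal reading, q = 0.** The formula reduces to ASD = √[2p/(1 − p)]. Setting it to 0.1 gives p = 0.01/2.01 = 0.4975%, or 19.9 of 4,000.

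- 19 of 4,000: ASD 0.098
- 20 of 4,000: ASD 0.100 (0.1003)
- p = 1%, 5%, 10%, 20%: ASD 0.14, 0.32, 0.47, 0.71

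**Step 3. Narrow reading, q > 0.** The Tio/Olo cell holds only other products and the comparator cell only Tio/Olo. Solving ASD = 0.1 for p > q:

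- q = 1%: p = 2.27% (first passed at 91 of 4,000)
- q = 2%: p = 3.66% (147 of 4,000)
- q = 5%: p = 7.41% (297 of 4,000)
- p = q: ASD 0.00, although the two cells have no product in common

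**Step 4. The free-combination rows.** SAP 7.2.2 does not define them. SAP 7.1 defines the free form of exposure as same-day prescription. If that definition carries over to the LAMA+LABA free-combination row, every patient counted there also meets the wider 30-day rule in exclusion 1, so on the literal reading the comparator cell is again 0%. The ICS+LAMA+LABA free-combination row is 0% only if it too is defined no more widely than the 30-day rule.

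**Step 5. What equal washouts would do.** With no LAMA+LABA allowed in either cohort, the FDC row is 0% against 0% and its ASD is 0/0, not estimable. A restricted comparison therefore does not make this row informative. Its use is to put the remaining rows under one washout.

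**The case against.** The difference is openly stated. Each cohort's criteria are listed in full, and inclusion 4 says the look-back serves to identify new use of the study drugs. On the narrow reading each cohort is washed out for its own products, which is a parallel and defensible design. Admitting patients who switch from another LAMA/LABA fits the aim of describing everyone who starts Tio/Olo, and switching is itself a form of channelling. Table 3 has 55 data rows by my count (10 prior COPD treatments, 4 other respiratory drugs, 18 exacerbation, 6 hospitalization, 7 comorbidity, 1 Charlson index, 9 medication history), and only one is affected outright. In the visible text an ASD above 0.1 triggers no matching, adjustment or decision. Crossing 0.1 at 20 patients follows from fixing one cell at zero; it does not show that a misleading result is likely.

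Most of this stands and sets the weight of the point. A reader might infer that the plan contradicts itself, since the protocol calls the criteria similar and the SAP gives both cohorts a one-year look-back. The documents do not support that: similar is not identical, and a look-back of equal length does not imply the same drugs. A reader might also infer one-sided selection into the Tio/Olo cohort; that holds only on the literal reading.

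The objection does not rescue the row. A legitimate product-specific washout still leaves two cells that cannot be compared, and SAP 10.1 makes no exception for them.

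**Conclusion.** The point holds as a minor one. On either reading of comparator exclusion 1, the prior LAMA/LABA FDC row does not compare like with like, and its ASD should not be interpreted. On the literal reading about 0.5% of Tio/Olo patients (20 of 4,000) is enough to pass the threshold. On the narrow reading the ASD can be large or zero without saying anything about the same drugs. The free-combination rows are affected only under the definitions in Step 4.

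The size rests on assumed shares, an assumed ASD formula and the protocol's approximate cohort size. It is tempting to go on to say that the severity, comorbidity or co-medication rows are distorted, or that the safety results are. The documents do not show the first, and the second does not follow: the incidence rates are computed within the Tio/Olo cohort alone. Nor can one say that a same-washout comparison is absent. SAP 10.2, the patient selection figure, the SAP pages after Table 3 (23 to 27) and Protocol 9.7.2, which the ENCePP checklist cites for stratified and sensitivity analyses, are not visible in the public version.

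**What to change.** 1. In SAP 6.3, state whether comparator exclusion 1 includes Tio+Olo.
2. In Table 3, define the free-combination rows, mark the prior LAMA/LABA rows as determined by the exclusion criteria, and exempt them from the 0.1 rule. Report the share of Tio/Olo starters with prior use of another LAMA/LABA as a description only.
3. Unless a non-visible section already does so, add a supplementary baseline comparison restricted, in both cohorts, to patients with no LAMA+LABA in the prior year (Tio+Olo included, free or fixed), and judge channelling among new users from it.

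Keep the full Tio/Olo cohort for the primary incidence rates and for its own baseline description.

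The cost is some SAP wording, one filter and one or two columns on data already held. The supplementary comparison loses some Tio/Olo patients: at assumed switcher shares of 5%, 10% and 20%, it keeps 3,800, 3,600 and 3,200 of 4,000. Taking the standard error of an ASD near zero as √(1/n₁ + 1/n₂), with an assumed 4,000 comparators, it rises from 0.0224 with the full cohort to 0.0227, 0.0230 and 0.0237. Any loss of comparators on the narrow reading would add to this and cannot be sized from the documents.
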